Four secondary outcomes for YP are making use of standard administrative data collected for the SSDA903. We expect to have close to complete data on these outcomes for all YP who stay in foster care.

Table 1: Trial design

Trial design, including number of arms		Two-armed cluster randomised controlled trial
Unit of randomisation		Young person’s social worker (YPSW)
Stratification variables (if applicable)		Local Authority (LA)
Primary outcome	variable	Young person’s externalising behaviour
	measure (instrument, scale, source)	Externalising score, Strengths and Difficulties Questionnaire (Goodman, Meltzer & Bailey, 1998), carer-reported version, fielded in online survey 10-12 months after baseline
Secondary outcome(s)	variable(s)	Young person: SDQ Internalising and Prosocial sub-scales; Involvement with criminal justice system; transition into residential care, placement stability; missing from care episodes SSW / YPSW: Attitudes to trauma-informed practice FCs: compassion satisfaction, burnout; secondary traumatic stress; attitudes to trauma-informed practice
	measure(s) (instrument, scale, source)	Young person: SDQ, carer-report version; Child conviction or subject to youth caution (SSDA903 2024-25); transition into residential care (SSDA903 2024-25); unplanned moves (SSDA903 2024-25); missing from care episodes (SSDA9035 2024-25). SSW / YPSW: ARTIC scale at 12 month after baseline FCs: Professional Quality of Life Scale (self-report), bespoke questionnaire (self-report) at 10-12 months after baseline
Baseline for primary outcome	variable	Young person’s externalising behaviour
	measure (instrument, scale, source)	Externalising score, Strengths and Difficulties Questionnaire, carer-report (Goodman et al, 1998), fielded in online survey as close as possible to randomisation of YPSW

Baseline for secondary outcome	variable	
Young person: Emotional and behavioural difficulties; Involvement with criminal justice system; Transition into residential care, placement stability; missing from care episodes
 
SSW / YPSW: Attitudes to trauma-informed practice
 
FCs: compassion satisfaction; burnout; secondary traumatic stress; attitudes to trauma-informed practice

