This approach to randomisation does not give a four-arm RCT with balance across all four arms. Analysis Arms 1 and 2 will be balanced (which is vital for the primary analysis), and Arms 3 and 4 will be balanced, but the YP in Arms 3 and 4 will have different experiences to those in Arms 1 and 2 in the sense that the Arms 3 and 4 YP will be more likely to have a YPSW and SSW who work together infrequently. This does not affect the primary analysis, which compares just Arms 1 and 2, but in the exploratory analysis that compares all four arms the lack of balance will be acknowledged.

Once randomisation has been completed, each young person will have been assigned to one of the four randomisation arms. Some contamination during the trial is inevitable (with some 'control' YP being assigned to a trained social worker during the trial and vice versa). This will be monitored and sensitivity analysis will be conducted to establish the degree to which this dilutes the overall effect sizes (see analysis section).

Sample size calculations overview

Our primary analysis (which uses externalising behaviour as measured through the SDQ as an outcome) focuses on the YP where both the YPSW and SSW have either been assigned to the intervention group or to the control group (Analysis Arms 1 and 2 as described in the randomisation section above). Arms 1 and 2 between them cover 66% of all the eligible YP identified as in-scope for the trial.

Table 2 sets out the MDES and sample sizes that were originally anticipated and as they were presented in version 1 of the trial protocol. The final column sets out our revised estimates after recruitment of LAs, baseline data collection, and randomisation. The original intention was to recruit 10 LAs to the trial rather than the eight achieved, and the initial predictions of response rate at baseline proved too optimistic. However, the number of social workers was much larger than anticipated, which reduces the average cluster size. Nevertheless, the MDES

has increased from the initial protocol estimate of 0.21 standard deviations to 0.24 standard deviations.

The assumptions behind the calculations are:

- Across the eight LAs, the total number of eligible YP is 1,477. Of these, 979 have been assigned to one of the two primary analysis arms: 458 to the group where both the YPSW and the SSW are assigned to the intervention group and 521 to the group where both the YPSW and the SSW are assigned to the control group.

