where

n_1 is the achieved sample size in the intervention arm (Group 1);

n_2 is the achieved sample size in the control arm (Group 2);

m is the average cluster size;

ρ is the ICC; and

R is the correlation between the baseline and follow-up score.

The value 1.96 is the z-value for a type 1 error rate (alpha) of 0.05, and 0.84 is the z-value for 80% power.

Table 2 sets out the assumptions for the primary outcome (externalising SDQ score). The assumptions do not all hold for the secondary outcomes, the major differences being:

- For SSDA903 outcomes which are collected via administrative systems, the sample sizes will be somewhat larger because losses to the sample will be lower. The correlation between baseline and follow-up is not known but is likely to be low for the non-SDQ scores at least, and the ICC is not known, but overall we expect an MDES of around 0.20sd for these outcomes;
- There will be fewer FCs than YP in the analysis as FCs may care for more than one eligible YP, our best current assumption being that it will be around 139 in Group 1 and 163 in Group 2. We estimate an MDES of 0.27sd for their outcomes.
- There are 422 YPSWs and 264 SSWs in the trial (686 overall), divided into two groups, intervention and control, with around 316 in the intervention arm and 370 in the control arm per arm (139 and 163 respectively after non-response). For their outcomes we estimate an MDES of around 0.23sd.

Table 2: Sample size calculations

	Protocol version 1	Post randomisation
Minimum Detectable Effect Size (MDES)	0.21 sd	0.24 sd

		Protocol version 1	Post randomisation
Pre-test/ post-test correlations	level 1 (participant)	0.6	0.6
	level 2 (cluster)	0	0
Intracluster correlations (ICCs)	level 1 (participant)	0	0
	level 2 (cluster)	0.2	0.2
Alpha ⁷		0.05	0.05
Power		0.8	0.8
One-sided or two-sided?		Two	Two
Average cluster size		7.7	1.5
Number of clusters ⁸	intervention	70 YPSWs	198 YPSWs/124 SSWs at randomisation stage
	control	70 YPSWs	224 YPSWs/140 SSWs at randomisation stage
	total	140 YPSWs	422 YPSWs/264 SSWs
Number of participants	intervention	540	183 (after non-response)
	control	540	208 (after non-response)
	total	1,080	391

⁷ Please adjust as necessary for trials with multiple primary outcomes, 3-arm trials etc. when a Bonferroni correction is used to account for family-wise errors.

⁸ Please adjust as necessary e.g., for trials that are randomised at the setting, practitioner or participant level.

Analysis

Primary outcome analysis

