- The regression model for social worker outcomes will be specified using the primary outcome model, but there will be no clustering effects for YPSWs given that these are the units of randomisation. Here the model will be:

$$Y_{jk} = \beta_0 + \beta_1 Group_{jk} + \beta_2 X_{jk} + \beta_3 LA_k + \varepsilon_{jk} \quad (\text{Eq 3})$$

where

Y_{jk} = ARTIC score at follow-up for SW j within LA k;

$\beta_0, \beta_1, \beta_2, \beta_3$ = fixed effect parameters;

$Group_{jk}$ = indicator variable for group allocation (0=control; 1=intervention) within LA k;

X_{jk} = baseline ARTIC score for SWj within LA k;

LA_k = a vector for the local authority dummy variables, of which there will be seven. β_3 is a coefficient vector for the LA dummy covariates;

ε_{jk} = residual error term.

Given the large number of secondary outcomes, the secondary outcome tests for YP will be corrected for multiple comparisons using Hochberg's step-up procedure⁹. Likewise, but independently, the tests for the four secondary outcomes for FCs will be corrected.

Subgroup analyses

The trial is relatively small, with an expected sample size of under 210 per arm with complete baseline and follow-up data on the primary outcome. There are no prior expectations of large differential impacts across sub-groups of YP, and the sample size is too small for modest differences across groups to be identified. For these reasons, very little sub-group analysis is planned. The exception is that the primary YP outcome will be presented split by ethnic group (generated by running separate regression models per sub-group) to facilitate future meta-analysis, but excluding any ethnic groups with less than 30 YP per arm.

For the secondary social worker outcome, ARTIC, a joint YPSW/SSW analysis will be undertaken but, subject to some evidence of impact, separate models will be run and presented for YPSWs and SSWs.

Further analyses of the primary trial data

Sensitivity of the effect sizes to changes in YP and FC social workers during the trial

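### The minimum detectable effects quoted for the SSDA903 and foster carer outcomes assume alpha 0.05 per test, but the plan tests those outcomes with Hochberg's correction

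*SAP*

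**What the plan says.** The SAP's sample size section gives one formula for the minimum detectable effect size (MDES) and fixes its error rates: "The value 1.96 is the z-value for a type 1 error rate (alpha) of 0.05, and 0.84 is the z-value for 80% power". It then lists how the secondary outcomes differ from the primary outcome.

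- **SSDA903 outcomes.** "the sample sizes will be somewhat larger because losses to the sample will be lower". The baseline correlation is described as unknown but probably low, and the ICC as unknown. The conclusion is "overall we expect an MDES of around 0.20sd for these outcomes". No sample size, cluster size, ICC or correlation is attached to that figure.
- **Foster carer (FC) outcomes.** About 139 and 163 carers are expected. "We estimate an MDES of 0.27sd for their outcomes".

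Alpha is not among the listed differences. The secondary outcome analysis section nevertheless states that "the secondary outcome tests for YP will be corrected for multiple comparisons" by Hochberg's step-up procedure, and that the four FC tests are corrected as a separate family. The same section counts six secondary outcomes for young people (YP), four of them from SSDA903.

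**The concern.** An MDES is the effect at which the planned test has the stated power. Here it is computed for one test at 0.05, while the planned test is one of six, or one of four, under a family-wise correction. The quoted values therefore describe a more lenient test than the one that will be run.

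A second difficulty affects the SSDA903 figure. The cluster size of 1.5 used for the primary outcome is justified by survey non-response. For the administrative outcomes the data collection section says "We expect to have close to complete data on these outcomes for all YP who stay in foster care", so that reason does not carry over and clusters will be larger.

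At stake is how null results are read. A non-significant finding on unplanned moves, residential care, justice involvement or missing episodes could be taken to rule out effects of 0.20 sd with 80% power when the power is lower.

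**Working it through.** **Formula (SAP).** MDES = (z + 0.84) × √[(1/n₁ + 1/n₂) × (1 + (m − 1)ρ) × (1 − R²)], with z = 1.96.

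**Step 1: reproduce the plan's figures.**
- Primary: n = 183/208, m = 1.5, ρ = 0.2, R = 0.6. 2.8 × √(0.010272 × 1.1 × 0.64) = 0.238 (stated 0.24).
- FC: n = 139/163, with the primary m, ρ and R carried over. 2.8 × √(0.013329 × 1.1 × 0.64) = 0.271 (stated 0.27).
- SSDA903: cannot be reproduced strictly, because no inputs are stated.

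The FC match shows that its figure is at alpha 0.05, as the formula says.

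**Step 2: effect of the correction.** This step needs no assumption about n, m, ρ or R, because only z changes. Hochberg's thresholds run from 0.05 down to 0.05/k.
- k = 6: z at 0.05/6 is 2.638. Ratio (2.638 + 0.84)/2.8 = 1.242, so 0.20 becomes 0.248.
- k = 4: z at 0.05/4 is 2.498. Ratio (2.498 + 0.84)/2.8 = 1.192, so 0.271 becomes 0.323.
- Intermediate step, threshold 0.05/2: z = 2.241, ratio 1.10, so 0.20 becomes 0.220.

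**Step 3: power at the quoted effect sizes.** I simulated Hochberg's procedure on normal test statistics. Each real effect was set to have 80% power at 0.05, with correlations of 0, 0.3 and 0.5 between tests. Power for a given real effect was:

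| Family | Only one effect real | All effects real |
|---|---|---|
| Six YP outcomes | about 57% | about 69–71% |
| Four FC outcomes | about 62% | about 73–75% |

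Power falls short of 80% in both situations.

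**Step 4: SSDA903 figure before correction.** Inputs from the SAP:
- Arm sizes: 458 YP in Arm 1 (pure intervention), 521 in Arm 2 (pure control), 979 in all.
- Clusters: 422 YPSWs, so 979/422 = 2.32 YP each. The SAP's own 3.7 is YP per SSW (979/264 = 3.71).

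Assumptions made here: ρ = 0.2, borrowed from the SDQ externalising score; R = 0, standing for a low correlation; and cluster size falling in proportion to the share of YP retained.

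At full n, 1/458 + 1/521 = 0.004103:
- m = 2.32: 2.8 × √(0.004103 × 1.264) = 0.202.
- m = 3.7: 2.8 × √(0.004103 × 1.54) = 0.223.

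| YP retained | YPSW clusters, 0.05 | SSW clusters, 0.05 | YPSW clusters, 0.05/6 | SSW clusters, 0.05/6 |
|---|---|---|---|---|
| 100% | 0.202 | 0.223 | 0.250 | 0.276 |
| 90% | 0.209 | 0.229 | 0.259 | 0.284 |
| 80% | 0.217 | 0.237 | 0.270 | 0.294 |

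The SAP does not state the share retained. It excludes YP who leave foster care entirely, except for outcomes that capture moves, so some loss is to be expected for the justice and missing-episode outcomes.

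**The case against.** The strongest reply is that 0.20 contains no arithmetic error, and that is right. A reader might infer that 0.20 contradicts the SAP's own inputs. The document does not support this. It calls the ICC for these outcomes unknown, and its 0.2 belongs to the SDQ externalising score. The 3.7 counts YP per SSW, whereas the planned model clusters on YPSW. With 2.3 YP per YPSW, ICC 0.2 and R = 0, the formula gives 0.202 at full sample. Other admissible inputs also reach it: R = 0.3 with YPSW clusters gives 0.199 at 90% retained, and ICC 0.1 with m = 3.7 gives 0.202 at full sample. Even m = 1.5 would give 0.188 at full sample, although its justification is absent here.

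It is also fair to say that Hochberg is a step-up procedure, so 0.05/6 is its strictest threshold and does not apply in every case. The corrected values are therefore upper ends. Even so, Step 3 shows that power stays below 80% when every effect in the family is real.

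Finally, the SAP states its alpha openly, the figure is hedged, no decision depends on it, and results will carry confidence intervals. Quoting a per-test MDES is a defensible convention if labelled as such. Here the reader is not told that the planned test is stricter.

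**Conclusion.** The point holds in a limited form. The SSDA903 and FC figures are not 80%-power effect sizes under the plan's own testing rule. The shortfall is up to about a quarter of the SSDA903 value (0.20 to about 0.25) and about a fifth of the FC value (0.27 to about 0.32) at the strictest steps, with smaller increases at the others. This conclusion does not depend on ICC or cluster size. The single social worker outcome is not in a corrected family, so its figure is untouched by this point.

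Before correction, 0.20 is reachable but sits at the optimistic end of about 0.20 to 0.24. That range assumes ICC 0.2, R near 0 and 80% to 100% of YP retained.

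A reader might go further and conclude that the SSDA903 outcomes are worse powered than the primary outcome even without correction. The figures do not show that: all six uncorrected values, 0.202 to 0.237, lie below the unrounded primary value of 0.238. The order reverses at the strictest Hochberg step, where all six values are 0.25 or more.

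**What to change.** In the sample size section:

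1. State the n, m, ICC, R and alpha assumed for the SSDA903 outcomes, marking the ICC and R as assumptions.
2. Restate their MDES as about 0.20–0.24 sd uncorrected, and about 0.25–0.28 sd at the strictest Hochberg step with full n.
3. Restate the FC MDES as 0.27 sd uncorrected and up to 0.32 sd corrected.
4. Add alpha to the listed differences between primary and secondary outcomes.

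Percentage-point equivalents for the four binary outcomes would help readers but are optional, because the SAP gives no event rates to base them on.

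The cost is wording only. Design, sample and analysis stay as they are; the quoted figures become less favourable.

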The analysis of the efficacy trial data will be on an intention-to-treat basis. Estimates of impact per outcome will be based on a multilevel linear regression model with two levels, YPSW and YP, with the baseline version of each outcome being entered as a covariate. LA will be entered as a fixed effect. The analysis will be conducted in SPSS v28.0.1.1 via the MIXED procedure.

If, after non-response, we have data that is essentially unclustered then a single-level model will be fitted.

Primary outcome analysis

The primary outcome measure for YP in the trial is the SDQ externalising score.

The SDQ questionnaire includes five subscales, each with five items, that measure: 1. Emotional symptoms; 2. Conduct problems; 3. Hyperactivity/inattention; 4. Peer problems; 5. Prosocial behaviour. FCs score from 0 to 2 on each item using a scale 'not true', 'somewhat true' or 'certainly true', thus producing a score for each subscale from 0 to 10, where a lower total score is a better outcome for subscales 1-4, and the reverse for subscale 5 (prosocial behaviour). The 'externalising' score (from 0 to 20), is generated by summing the scores of the conduct and hyperactivity subscales.

The calculation of the externalising score will follow the standard SDQ scoring rules. The score will only be calculated where both subscales have a valid score (that is, at least three of the five items have been answered), others being set to missing. Each subscale will be calculated as (total subscale score)*5/(number answered).

The main regression model specification is as follows:

$$Y_{ijk} = \beta_0 + \beta_1 \text{Group}_{jk} + \beta_2 X_{ijk} + \beta_3 LA_k + u_{ijk} + \varepsilon_{ijk} \quad (\text{Eq 1})$$

where

Y_{ijk} = externalising score at follow-up for young person i belonging to assigned at baseline to YPSW j within LA k;

$\beta_0, \beta_1, \beta_2, \beta_3$ = fixed effect parameters;

Group_{jk} = indicator variable for group allocation of the YP's YPSW and SSW (0=control; 1=intervention) within LA k;

X_{ijk} = baseline externalising score for young person i assigned at baseline to YPSW j within LA k;

LA_k = a vector for the local authority dummy variables, of which there will be seven. β_3 is a coefficient vector for the LA dummy covariates;

u_{ij} =random effect for i th member of YPSW j ;

ε_{ijk} = residual error term for i th member of cluster j .

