The characteristics shown will be: YP randomised per LA, gender, age, ethnic group, SDQ externalising mean at baseline, and SDQ internalising and prosocial score means at baseline.

Missing data

We will describe and summarise the extent of missing data per outcome, and the reasons for data being missing where known will be reported on. We will document how much missing data is unit non-response and how much is item non-response, and whether there is evidence for trial imbalance because of missing data either at baseline or follow-up.

The primary ITT regression analysis will be based on complete cases, that is those for which all of the variables needed for the model are complete. The implicit assumption here is that missing data at follow-up is 'missing completely at random' (MCAR). However, because the rate of missing data in this trial is inevitably high (because of non-response to the surveys by FCs either at baseline or follow-up), we will assess the sensitivity of the results to alternative assumptions about the mechanisms leading to missing data.

¹¹ We ruled out analysis that tries to control for these switches because we will not have rich enough data to know when during the trial period the switch occurred, and because of the additional complexity introduced because both or just one of the professionals could be switched

Firstly, we will use the baseline outcome variables for YP and FCs¹², together with other YP and FC characteristics to model (via a logistic regression) the probability per YP of a case being in the intervention arm rather than the control arm. This will identify any observable predictors of imbalance, and the regression model (Eq 1) will be re-run to include, as covariates, any significant predictors that are identified from this logistic regression. This will help establish whether the effect sizes are influenced by the level and nature of missing data, under an assumption of missing at random (MAR).

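### Near-free improvement, not an error: prespecify age, gender and the other baseline SDQ scores in Eq 1/Eq 2, and a worker-role term in Eq 3

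*SAP*

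**What the plan says.** **Primary model.** SAP, Analysis, Primary outcome analysis: the models are fitted "with the baseline version of each outcome being entered as a covariate", and "LA will be entered as a fixed effect". Eq 1 contains group, baseline externalising score, seven LA dummies and a YPSW random effect. Eq 2, used if the average cluster size is 1.1 or below, drops the random effect and keeps the same covariates.

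**Other baseline data held.** SAP, Imbalance at baseline and follow-up: "The characteristics shown will be: YP randomised per LA, gender, age, ethnic group, SDQ externalising mean at baseline, and SDQ internalising and prosocial score" means. These variables are tabulated by arm.

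**The one route into the model.** SAP, Missing data: YP and carer baseline variables go into a logistic regression for arm. Eq 1 is then re-run with "any significant predictors that are identified from this logistic regression" added. This is a sensitivity analysis under MAR. The primary analysis is complete-case, with an implicit MCAR assumption.

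**Social workers.** SAP, Secondary outcome analysis: "The regression model for social worker outcomes will be specified using the primary outcome model, but there will be no clustering effects for YPSWs". Eq 3 contains group, baseline ARTIC and LA. SAP, Subgroup analyses: "a joint YPSW/SSW analysis will be undertaken", and then, "subject to some evidence of impact, separate models will be run and presented for YPSWs and SSWs".

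**The concern.** Baseline variables that predict the follow-up score reduce residual variance and need no further recruitment. The trial expects 391 analysed young people, and its MDES has moved from 0.21 to 0.24, so unused baseline information deserves a look.

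Missing data add a second reason. Of 979 young people in Arms 1 and 2, 588 (60%) are expected to fall outside the complete-case analysis. Conditioning on variables that predict both response and outcome weakens the assumption on which the primary estimate rests. The SAP's selection rule does not look for such variables. Significance for predicting arm finds observed imbalance, and a strongly prognostic covariate that is balanced between arms would never be chosen. The selection also depends on the data, although a fixed list could be named now. That matters more because the Randomisation section says the analyst is not blind to allocation.

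In Eq 3 the two professions are pooled with no term for the one known difference between them. If the joint ARTIC result shows no sign of impact, no model will account for role.

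**Working it through.** **Inputs from the SAP (Sample size calculations overview and Table 2):** n1 = 183, n2 = 208, m = 1.5, ICC = 0.2, R = 0.6 (R-squared 0.36), multiplier 1.96 + 0.84 = 2.8. Social workers in Table 2: 198 YPSWs and 124 SSWs in the intervention arm, 224 and 140 in control.

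**Not in the SAP, assumed here:** a gain in R-squared of 0.02 to 0.06 beyond the baseline score; an ARTIC gap between roles, after baseline ARTIC, of 0.1 to 0.4 sd; a 10-point difference between arms in the SSW share of respondents.

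**1. Reproduce the stated MDES.** The formula is MDES = 2.8 × √[(1/n1 + 1/n2) × (1 + (m − 1) × ICC) × (1 − R²)].
- 1/183 + 1/208 = 0.010272, and the design effect is 1 + 0.5 × 0.2 = 1.1.
- 2.8 × √(0.010272 × 1.1 × 0.64) = 0.238, stated as 0.24.
- With R = 0.53 the result is 0.252 (stated 0.25). Protocol version 1, with 540 per arm and m = 7.7, gives 0.209 (stated 0.21).

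The stated precision therefore matches Eq 1, with the baseline score as the only source of R-squared.

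**2. Add prognostic covariates.** The equivalent number of extra young people is 391 × (0.64/(0.64 − gain) − 1).

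| R² | Gain | MDES | Equivalent extra YP |
|---|---|---|---|
| 0.36 | 0 | 0.238 | 0 |
| 0.38 | 0.02 | 0.234 | 13 |
| 0.42 | 0.06 | 0.227 | 40 |

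If the correlation is 0.53, the same gains move the MDES from 0.252 to between 0.249 and 0.242.

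**3. Could this restore 0.21?** The R-squared needed is 1 − (0.21/2.8)²/(0.010272 × 1.1) = 0.50, which is 0.14 above 0.36. Even a gain of 0.10 gives only 0.219.

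**4. Role balance at randomisation.** The SSW share is 124/322 = 38.5% in the intervention arm and 140/364 = 38.5% in control.

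**5. What the role term could do in Eq 3.**
- *Precision.* With an SSW share of 38.5% and residual variance taken as 0.64 (borrowed from the SDQ calculation), a remaining role gap of 0.1 to 0.3 sd lowers the MDES by 0.2% to 1.6%.
- *Protection.* If the SSW share among respondents differed by 10 points between arms, and roles still differed by 0.2 to 0.4 sd, leaving role out would shift the effect by 0.10 × 0.2 to 0.4 = 0.02 to 0.04 sd. The standard error implied by the stated ARTIC MDES is 0.23/2.8 = 0.08 sd.

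**The case against.** The strongest answer is that Eq 1 is a complete and valid prespecification. It adjusts for the baseline outcome and the stratifier, and the power calculation assumes that model, so no promised precision is lost. That stands.

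A reader might infer that covariate choice caused the MDES to worsen, or that wider adjustment would win back the loss. Neither is supported. The SAP links the rise to fewer LAs and lower baseline response, and step 3 shows that plausible gains fall short. A reader might also infer that the primary estimate is biased. Leaving covariates out of a linear model does not bias a randomised comparison when data are complete.

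The missing-data argument has limits. The 588 are not all non-respondents, because the 70% assumed at follow-up combines still being in foster care with completing the survey, and leavers are excluded by design. The SAP already plans the adjusted re-run, a respondent versus non-respondent comparison using SSDA903 SDQ, and bounds if MNAR is indicated. The logistic regression is offered as a check on imbalance, and for that job the rule is coherent. What remains is that no part of the plan conditions on a fixed set of likely predictors of outcome.

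It is tempting to ask for the SSDA903 SDQ and carer burnout as covariates too. The SAP does not support requiring them. The SSDA903 score is a total score, leaves out those over 16 and those looked after for less than 12 months, and is collected at varying times. Nothing in the SAP shows that burnout predicts the outcome.

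On Eq 3, role is balanced at randomisation, baseline ARTIC will absorb much of any stable role difference, and role-specific models are planned, though conditionally. Social-worker response should not be taken as firmly 44% (302 of 686). The counts behind it, 139 and 163, are identical to the foster-carer counts in the preceding bullet and may be a slip.

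**Conclusion.** This is an optional improvement at very low cost, and not an error or contradiction in the SAP. The description of Eq 1, Eq 2 and Eq 3 is certain; the size of the benefit is not. On an assumed R-squared gain of 0.02 to 0.06, the primary MDES moves from 0.238 to between 0.234 and 0.227. If the other baseline scores add almost nothing beyond the externalising score, the gain is close to zero.

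For Eq 3 the precision gain is negligible. The case for the role term is protection against non-response that differs by role and arm, and the possible shift is at most about half a standard error under the assumed values. The documents do not show that such a shift will occur.

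**What to change.** Before outcomes are seen:

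- Add age, gender, and baseline SDQ internalising and prosocial scores to Eq 1 and Eq 2 as prespecified covariates.
- State a simple imputation rule for missing values of these added covariates, for example the mean plus a missing indicator, so that no case leaves the complete-case set because of them.
- Keep the current Eq 1 as a named sensitivity analysis.
- Add a YPSW/SSW indicator to Eq 3, whether or not the role-specific models are later run.

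The cost is a few lines of SAP text, a few degrees of freedom out of about 391 in the primary model and one in Eq 3, and a slightly longer primary model. No new data are needed. The SSDA903 SDQ and carer burnout need not be added.
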